### **9.1.1.1 Repetition of Screening Assessments**

#### **Parts A and B**

Screening assessments may be repeated once to establish study eligibility. If repeat values of the individual assessment(s) are within the eligibility criteria and completed within the screening window, then the subject is eligible for the study.

### **9.1.1.2 Rescreening**

#### **Parts A and B**

Subjects may be rescreened once. If a subject is rescreened, the subject will provide informed consent and assent (as applicable), and all screening assessments will be repeated, except for:

- *CFTR* genotyping
- Ophthalmologic examination (if performed within 3 months before the date of informed consent)

If a subject is rescreened, a new screening window will begin when the first rescreening assessment has been initiated.

### **9.1.1.3 Extension of Screening Period Window**

#### **Parts A and B**

A subject may have the Screening Period window extended by 2 weeks for the following reasons:

- Repetition of the Screening Period assessments (Section 9.1.1.1)
- Unexpected operational or logistic delays, or to meet the eligibility criteria
- Scheduling of ophthalmologic examination (Section 11.5.5)

## **9.1.2 Treatment Period**

### **Parts A and B**

The Treatment Period will last approximately 15 days in Part A and 24 weeks in Part B. Study drug administration details are provided in Section 9.6.

Subjects who prematurely discontinue study drug treatment will remain in the study from the time of discontinuation of study drug treatment through the last scheduled study visit and complete the assessments for all study visits, as described in Section 9.1.4.

### 9.1.3 Follow-up

#### Part A

Subjects will have a Safety Follow-up Visit 28 ( $\pm$  7) days after the last dose of study drug.

#### Part B

The Safety Follow-up Visit is scheduled to occur 28 ( $\pm$  7) days after the last dose of study drug for subjects who complete study drug dosing and for subjects who prematurely discontinue study drug dosing, as described in Section 9.1.4.

An optional open-label extension safety study will be available for subjects who complete the last treatment period visit and are eligible. The Safety Follow-up Visit is not required for subjects who complete the Week 24 Visit and enroll in the optional open-label extension safety study within 28 days after the last dose of study drug.

### 9.1.4 Early Termination of Treatment

#### Parts A and B

If a subject prematurely discontinues study drug treatment, an Early Termination of Treatment (ETT) Visit should be scheduled as soon as possible after the decision to discontinue treatment. Subjects who prematurely discontinue treatment will also be required to complete the Safety Follow-up Visit ([Table 3-2](#) for Part A and [Table 3-4](#) for Part B), if applicable (Section 9.1.3).

If a subject withdraws from the study and also withdraws consent or assent, no further assessments will be performed. Vertex may retain and continue to use any data and samples collected before such withdrawal of consent or assent.

#### Part B

If the ETT Visit occurs 3 weeks or later following the last dose of study drug, then the ETT Visit will replace the Safety Follow-up Visit, and a separate Safety Follow-up Visit will not be required.

Subjects who prematurely discontinue study drug treatment will continue to complete all scheduled study visits for assessments following completion of the ETT Visit, as detailed in [Table 3-4](#).

Subjects who prematurely discontinue treatment in Part B are not eligible to enroll in the optional open-label extension safety study.

### 9.1.5 Lost to Follow-up

#### Part B

A subject will be considered lost to follow-up if both of the following occur:

- The subject misses 2 consecutive study visits (telephone contact and/or clinic visit) and is subsequently unable to be contacted by telephone (3 documented attempts by telephone within 2 weeks following the second missed visit)
- The subject does not respond within 2 weeks to a registered letter sent after the 3 attempted telephone contacts.

### 9.1.6 Completion of Study Participation

Completion of study participation for each individual subject is defined as 1 of the following:

#### Part A

- For subjects who complete the Treatment Period: the Safety Follow-up Visit
- For subjects who prematurely discontinue study drug treatment but do not withdraw consent (and assent, as applicable): the latest of the Day 15 Visit, ETT Visit, or Safety Follow-up Visit
- For subjects who withdraw consent or assent: date of withdrawal of consent or assent, whichever is earlier (Section 9.9)

#### Part B

- For subjects who complete the Treatment Period and enter an open-label extension safety study within 28 days of the Week 24 Visit: the Week 24 Visit
- For subjects who complete the Treatment Period and do not enter an open-label extension safety study within 28 days of the Week 24 Visit: the Safety Follow-up Visit
- For subjects who prematurely discontinue study drug treatment but do not withdraw consent (and assent, as applicable): the latest of the Week 24 Visit, ETT Visit, or Safety Follow-up Visit (if required)
- For subjects who withdraw consent or assent: date of withdrawal of consent or assent, whichever is earlier (Section 9.9)

If subjects are lost to follow-up (Section 9.1.5), the date of completion of study participation will be defined as the date of the last contact.

The end of study is defined in Section 13.2.8.

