**Figure 9-2 Part B Study Design**

IVA: ivacaftor; TEZ: tezacaftor

- a The Safety Follow-up Visit is scheduled to occur 4 weeks ( $\pm 7$  days) after the last dose. This visit is not required for subjects who enroll in an optional open-label extension safety study within 28 days of the last dose.
- b Subjects who complete the visits in the Treatment Period, regardless of whether they are on a treatment interruption, will be offered the opportunity to enroll in an optional open-label extension safety study evaluating VX-445 in a triple combination regimen.

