**Table 9-3 Study Drug Administration, Part B**

Subject Weight at Day 1	Tablet Strength	Time	Number of Tablets Taken
<30 kg	50-mg VX-445/25-mg TEZ/37.5-mg IVA	AM	2 tablets
	75-mg IVA	PM	1 tablet
≥30 kg	100-mg VX-445/50-mg TEZ/75-mg IVA	AM	2 tablets
	150-mg IVA	PM	1 tablet

IVA: ivacaftor; TEZ: tezacaftor

Study drug should be administered with a fat-containing meal or snack, such as a standard “CF” meal or snack or a standard meal according to the following guidelines:

1. It is recommended that the dose be taken within 30 minutes of the start of the meal or snack.
2. All doses of study drug (morning and evening, as applicable) should be administered at approximately every 12 hours ( $\pm$  2 hours) on each dosing occasion (e.g., if the morning doses of study drug are administered at 08:00 hour on Day 1, all subsequent morning doses should be administered between 06:00 hour and 10:00 hour).
3. At the Day 1 Visit, all subjects will be observed for 4 hours after the morning dose of the study drug.
4. The date, amount taken, and time of study drug administration including whether food was taken with each dose, will be recorded for 2 days before PK sample collection and on the days of PK sample collection.
5. On days of scheduled visits (Day 1, Day 15, Weeks 4, 8, 12, and 16), the morning dose of study drug will be administered at the site after predose assessments have been completed. The meal or snack will be provided by the site for the morning dose of study drug.
6. For visits after the Day 1 Visit, subjects will be instructed to bring all used and unused study drug to the site; study drug will be dispensed at each visit, as appropriate.
7. At the Week 24 Visit, the morning dose of study drug will NOT be administered. The last dose of study drug will be the evening dose administered the day before the Week 24 Visit.

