## 12.3 Statistical Analysis

### 12.3.1 General Considerations

#### Parts A and B

Data from Part A and Part B will be analyzed separately.

**Continuous variables** will be summarized using the following descriptive summary statistics: number of subjects (n), mean, SD, median, minimum value (min), and maximum value (max). The precision of the measurement for each continuous variable will be specified in the SAP.

**Categorical variables** will be summarized using counts and percentages. Percentages will be presented to 1 decimal place.

**Treatment-emergent (TE) period** for Parts A and B will include the time from the first dose of study drug in the respective Part through 28 days after the last dose, or the completion of study participation date, whichever is earlier.

**Baseline** for Part A, unless otherwise specified, is defined as the most recent nonmissing measurement (scheduled or unscheduled) collected before the first dose of study drug in Part A. For ECGs, baseline will be defined as the most recent pretreatment measurement (or the average of replicate measurements, if the most recent pretreatment measurement is obtained in replicates) before the first dose of study drug. For sweat chloride, the baseline value will be the mean of assessment values on the left and the right arm at the most recent time point prior to the first dose of study drug. The measurement end time can be up to 30 minutes after dosing to be considered in the calculation for baseline sweat chloride. Baseline for Part B will be similarly defined.

**Absolute change** from baseline will be calculated as post-baseline value – baseline value.

**Relative change** from baseline will be calculated as (post-baseline value – baseline value)/baseline value.

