##### **13.1.1.3 Documentation of Adverse Events**

All AEs will be collected from the time the ICF is signed until the subject completes study participation, as defined in Section 9.1.6.

All subjects will be queried, using nonleading questions, about the occurrence of AEs at each study visit. When possible, a constellation of signs and/or symptoms will be identified as 1 overall event or diagnosis. All AEs for enrolled subjects will be recorded in the CRF and source document. AEs for subjects who are screened but not subsequently enrolled in the study will be recorded only in the subject's source documents. The following data will be documented for each AE:

- Description of the event
- Classification of “serious” or “nonserious”
- Date of first occurrence and date of resolution (if applicable)
- Severity
- Causal relationship to study drug(s)
- Action taken
- Outcome
- Concomitant medication or other treatment given

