9 STATISTICAL ANALYSIS

9.1 General Considerations

Part A and Part B

Data from Part A and Part B will be analyzed separately.

The Schedule of Assessments is provided in Section 3 of the CSP. The precision standards for reporting safety and efficacy variables are provided in an internal Biometrics document that specifies the programming rules including the precision for derived variables.

Continuous variables will be summarized using the following descriptive summary statistics: the number of subjects (n), mean, standard deviation (SD), median, minimum value (min), and maximum value (max).

Categorical variables will be summarized using counts and percentages. Percentages will be presented to 1 decimal place.

Baseline unless otherwise specified, is defined as the most recent non-missing measurement (scheduled or unscheduled) collected prior to the first dose of study drug in the corresponding Part.

Note: for subjects who take Orkambi or Symdeko (branded as Symkevi in Europe) during the 28 days before the screening visit, the data collected at screening visit will not be used for baseline derivation for spirometry, sweat chloride and LCI.

Absolute change from baseline will be calculated as Post-baseline value – Baseline value.

Relative change from baseline will be calculated and expressed in percentage as 100% × (Post-baseline value – Baseline value) / Baseline value.

Treatment-emergent (TE) Period for Part A and Part B will include the time from the first dose of study drug in the corresponding Part through 28 days after the last dose or the completion of study participation date in the corresponding Part, whichever occurs first.

Extended Treatment-emergent (TE) Period for Part B will include the time from the first dose of study drug in Part B through the completion of study participation.

For subjects who do not have unscheduled visit after the Week 24 visit, refer to Section 9.1.6 of the CSP for the definition of completion of study participation. For subjects who have unscheduled visit after the Week 24 visit, the completion of study participation is defined as the date of the last unscheduled visit.

Unscheduled visits: Unscheduled visit measurements will be included in analysis as follows:

- In scheduled visit windows per specified visit windowing rules

- In the derivation of baseline and last on-treatment measurements

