Height z-score and Weight z-score: the height z-score and weight z-score, adjusted for age and sex, will be referred to as weight-for-age z-score (weight z-score) and height-for-age z-score (height z-score). The weight z-score and height z-score will be calculated by using Centers for Disease Control and Prevention (CDC) growth charts⁸, with the age (in months) used for the calculation defined in [Appendix A](#).

Modified Facial Hedonic Scale: refer to Section 11.3.1 of the CSP for details.

Pulmonary exacerbation (PEX): A PEX is defined as a new or changed antibiotic therapy (intravenous [IV], inhaled, or oral) for any 4 or more of the following signs/symptoms:

- Change in sputum
- New or increased hemoptysis
- Increased cough
- Increased dyspnea
- Malaise, fatigue, or lethargy
- Temperature above 38°C (equivalent to approximately 100.4°F)
- Anorexia or weight loss
- Sinus pain or tenderness
- Change in sinus discharge
- Change in physical examination (PE) of the chest
- Decrease in pulmonary function by 10%
- Radiographic changes indicative of pulmonary infection

The **PEX analysis period** will include the time from the first dose date of study drug until the last efficacy assessment, which may be collected up to the Week 24 Visit or the earlier of Day 169 and the end of study participation if the subject does not have the Week 24 Visit.

The number of PEX through Week 24 is then defined as the total number of PEX during the PEX analysis period.

Lung clearance index (LCI): the LCI assessments are derived from N₂-multiple-breath washout (MBW) testing. Each MBW will be performed in multiple replicates for each visit and the final LCI value will be calculated from the technically acceptable washout replicates as graded and determined by a central reader. The following algorithm is used to derive the LCI values at each visit based on the multiple replicates:

- When there is only one acceptable replicate at the visit, the LCI values will not be calculated. The assessment for that subject at the corresponding visit will be missing.
- When there are 2 or more acceptable replicates at the visit, the mean of the values for the acceptable replicates will be calculated as the LCI value at the corresponding visit.

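### Part B children who enter the extension some days after Week 24 have a gap with no required AE collection and a post-dose TE window of 1 day instead of up to 28, and the 28-day rule has two different anchors

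*Protocol*

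**What the plan says.** - **Completion.** Protocol 9.1.6 (Part B) sets the completion date for children who finish the Treatment Period and "enter an open-label extension safety study within 28 days of the Week 24 Visit: the Week 24 Visit". Those who do not enter within that time complete at the Safety Follow-up Visit.
- **AE collection.** Protocol 13.1.1.3: "All AEs will be collected from the time the ICF is signed until the subject completes study participation, as defined in Section 9.1.6". Concomitant medications follow the same end date (9.5). After completion, 13.1.2.2 still asks for SAEs considered related to study drug.
- **Safety Follow-up.** Protocol 9.1.3 waives this visit for children who complete the Week 24 Visit and "enroll in the optional open-label extension safety study within 28 days after the last dose of study drug". Table 3-4 footnote b and Figure 9-2 footnote a also count from the last dose.
- **TE Period.** Protocol 12.3.1 runs it from the first dose "through 28 days after the last dose, or the completion of study participation date, whichever is earlier". SAP 9.1 agrees: "through 28 days after the last dose or the completion of study participation date in the corresponding Part, whichever occurs first". The SAP's Extended TE Period for Part B also ends at completion. If there is an unscheduled visit after Week 24, SAP 9.1 moves completion to the last such visit.
- **Last dose.** Protocol 9.6.1: "The last dose of study drug will be the evening dose administered the day before the Week 24 Visit".
- **Interruption.** Figure 9-2 footnote b says that children who complete the Treatment Period visits, "regardless of whether they are on a treatment interruption, will be offered the opportunity to enroll" in the extension.

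**The concern.** Completion is placed at the Week 24 Visit even when the child enters the extension days or weeks later. In between, the child is off drug, the Safety Follow-up Visit is normally waived, and this protocol no longer asks for AEs apart from related SAEs. Until a delayed child actually enters, the site cannot know which bullet of 9.1.6 applies, so the cut-off is fixed only in hindsight.

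AEs are part of the Part B primary endpoint. The AE tables cover TEAEs only and give numbers and percentages of subjects, without adjustment for time observed. A child who does not roll over contributes several weeks after the last dose, and a delayed rollover child contributes one day. Even if a gap event reaches the database, SAP 9.4.1 classes it as post-treatment, so it appears in a listing and not in the TEAE tables.

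The second issue is independent of the first. The 28-day rule has two starting points, so one section can end a child's participation while another still requires the Safety Follow-up Visit.

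**Working it through.** **The plan's own figure.** The only computed Part B figure on AEs is Protocol Table 12-1, with probability 1 − (1 − θ)^n. For n = 45 this gives 90.06% (θ = 5%) and 99.13% (θ = 10%); for n = 50, 92.31% and 99.48%. All four match the table. The point below does not depend on them.

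**Inputs.**
- Week 24 is Day 169. This is the target day in SAP Appendix A, and the PEx analysis period in SAP 9.3.2.2.1 uses the same day ("the earlier of Day 169 and the end of study participation if the subject does not have the Week 24 Visit").
- The last dose is the evening before, Day 168.
- TE end = min(last dose + 28, completion date).

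**Post-dose part of the TE Period.**
- Rollover child: min(168 + 28, 169) = min(196, 169) = Day 169. The tail is 169 − 168 = 1 day and the whole TE Period is 169 days.
- Without the completion cut-off: Day 196, a tail of 28 days. The difference is 196 − 169 = 27 days.
- Child who does not roll over: Safety Follow-up falls 28 ± 7 days after the last dose, so the tail is min(28, 21 to 35) = 21 to 28 days.
- At the edges of the ± 5-day visit window (Week 24 on Day 164 or Day 174) the rollover tail is still 1 day.
- Child on interruption whose last dose was k days before Week 24: the tail is k days, up to 28. The 1-day tail belongs to the usual case.

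**Days without required AE collection.** Full days strictly between the Week 24 Visit and the entry day, for entry d days after the visit, are d − 1 (0 if d = 0):

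| Entry, days after Week 24 | Entry day | Full days uncovered | Share of 28 |
|---|---|---|---|
| 0 | 169 | 0 | 0% |
| 7 | 176 | 6 | 21% |
| 14 | 183 | 13 | 46% |
| 20 | 189 | 19 | 68% |
| 28 | 197 | 27 | 96% |

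**Upper bound.** If all 45 expected completers rolled over with the longest gap, the loss would be 45 × 27 = 1,215 patient-days, or 1,215 / 365.25 = 3.3 patient-years. This is a ceiling and not an estimate.

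**The two clocks.**
- Usual case: counting from the last dose, entry qualifies up to Day 168 + 28 = 196. Counting from Week 24, it qualifies up to Day 169 + 28 = 197. They disagree for entry on Day 197 only. On that day 9.1.6 puts completion at Week 24, while 9.1.3 does not waive Safety Follow-up.
- Interruption, last dose 25 days before Week 24 (Day 144): the last-dose clock ends on Day 172 and the Week 24 clock on Day 197. They disagree for entry on Days 173 to 197, which is 25 days. Entry 10 days after Week 24 (Day 179) is 35 days after the last dose, so 9.1.6 ends participation at Week 24 and 9.1.3 still requires the visit.
- In general the clocks differ by the number of days between the last dose and the Week 24 Visit.

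**The case against.** The strongest reply has four parts.

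1. **The cut-off is deliberate.** The primary objective is safety through Week 24, both documents end the TE Period at completion, and this keeps extension exposure out of the Part B counts. It is indeed explicit and consistent. But the same TE Period runs up to 28 days past the last dose for children who do not roll over, so the plan does count off-drug events for some children. Ending the window at extension entry would also keep extension exposure out.

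2. **The gap may be covered elsewhere.** The extension protocol may collect AEs from its own consent, which could be signed at or near Week 24. That stands as a possibility that these documents neither confirm nor exclude. It would not by itself bring the events into the Part B TEAE tables.

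3. **There are exceptions.** Related SAEs stay reportable, AEs already begun are followed to outcome, and an unscheduled visit after Week 24 moves the SAP completion date. All of this is correct. However, 13.1.1.3 ties AE collection to Protocol 9.1.6 and not to the SAP's modified date.

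4. **The size is unknown and the clock conflict is rare.** Same-day rollover loses nothing, Part B has one arm with descriptive safety only, and the clocks usually differ by one day. In the 28-day row of the table, 9.1.3 would still require Safety Follow-up, so the longest gap on which both clocks agree is entry on Day 196, with 26 full days uncovered. This stands, and it limits the weight of the point.

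A reader might go further and infer that the TE Period itself shrinks to one day, or that gap AEs are lost altogether. Neither follows. The TE Period still starts at the first dose and lasts about 169 days, and the exceptions above and the unseen extension protocol rule out an absolute statement.

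**Conclusion.** The point holds in limited form. For a child who enters the extension after, but within 28 days of, the Week 24 Visit, this protocol requires no collection of non-serious AEs or unrelated SAEs between the visit and entry. In the usual dosing pattern the post-dose part of the TE Period falls from up to 28 days to 1. Uncovered time runs from none to 27 full days, depending on the delay.

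This rests on the last dose being taken the evening before Week 24, on no unscheduled visit after Week 24, and on nothing being assumed about the extension's AE collection. It is tempting to conclude that TEAE incidence is understated by a known amount. The documents do not support that, because they give neither the number of delayed children nor the length of their gaps.

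The contradiction over the 28-day rule stands on the text alone: one day in the usual case, and up to weeks for a child on interruption at Week 24. The passages need to be reconciled.

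**What to change.** For children who enter the extension after the Week 24 Visit date:

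- In Protocol 9.1.6, with matching wording in 9.1.3, require collection of AEs, SAEs and concomitant medications up to extension entry.
- In Protocol 12.3.1 and SAP 9.1, end the TE Period at the earlier of extension entry and 28 days after the last dose.
- Alternatively, if the extension already collects AEs from Week 24, say so and include those events in the Part B TEAE tables.

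Reconcile the 28-day rule to a single anchor in 9.1.3, 9.1.6, Table 3-4 and Figure 9-2. Which anchor to use is for the sponsor to decide.

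The cost is a few lines of text and one AE query per delayed child, by telephone or at the extension entry visit. Children who roll over on the day of the Week 24 Visit are unaffected.
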